Trial ID: ISRCTN16853684  
Version No: 1.0  
Date: January 27th 2026

## Revision history

Protocol version	Date of Issue	Summary of changes Describe all changes since the first final protocol.
Final protocol v1.0	2026-01-27	N/A

Trial ID: ISRCTN16853684  
Version No: 1.0  
Date: January 27th 2026

### 3 List of used acronyms and abbreviations

CT	Computed tomography
DMSC	Data Monitoring and Safety Committee
DP	Diastolic blood pressure
EA	Epidural analgesia
eCRF	Electronic Case Report Form
LAST	Local Anesthetic Systemic Toxicity
MIE	minimally invasive esophagectomy
NRS	Numeric Rating Scale
SAE	Serious adverse event
SP	Systolic blood pressure

Trial ID: ISRCTN16853684  
Version No: 1.0  
Date: January 27th 2026

## 4 Synopsis

Title:	BALANCE - paravertebral Block Analgesia vs. epidural: Assessing Novel Care in Esophagectomy - BALANCE trial
Trial ID:	ISRCTN16853684
Short background/Rationale/Aim:	
Cancer in the esophagus and gastroesophageal junction are devastating malignancies with a lethality of over 80 %. Surgical resection is the best chance for cure and this is a demanding thoracoabdominal procedure. Thoracic epidural analgesia (EA) is routine for optimization of pain control and improved mobilization and lung function. Recent studies show suboptimal success rate of pain management with EA. In addition, side effects such as increased use of vasopressor drugs, hypotension, and fluid retention may be detrimental to patients' outcomes, specifically regarding healing of a marginally circulated anastomosis. Increased use of minimally invasive techniques, with or without robot assistance, has also reduced the need for epidural analgesia. Paravertebral block and local/transabdominal plane block have good results in minimally invasive esophagectomy, but there is a paucity of randomized trials.

Primary objective:	To compare safety (superior-less anastomotic leak) of paravertebral block compared to the current routine of epidural analgesia in minimally invasive esophagectomy for malignant disease.
Secondary objectives:	To compare pain relief, complications, postoperative hypotension, surgical time and recovery duration, survival, and more between paravertebral and epidural analgesia in minimally invasive esophageal resection for cancer.
Primary endpoint:	Anastomotic leak assessed up to 30 days after surgery
Secondary endpoint:	Pain relief and patient-reported outcomes, day 1, 2, 3, 7 and 30. All other outcomes (see secondary objectives) defined on postoperative day 30 except survival, which will be followed for 5 years.
Trial design:	A Phase III, multicenter, open-label, randomized, controlled clinical trial comparing the paravertebral analgesia technique to standard epidural analgesia after resection for esophageal cancer.
Trial population:	Adult ( $\geq 18$ years of age) patients undergoing minimally invasive esophagectomy with gastric conduit reconstruction due to confirmed cancer (cT1 N+ or cT2-4a any N; M0-1).

Trial ID: ISRCTN16853684  
 Version No: 1.0  
 Date: January 27th 2026

Number of subjects:	550

## 5 Background and rationale

Esophageal cancer is one of the most prevalent cancers globally, with its incidence on the rise in the Western world, predominantly attributed to the increased occurrence of adenocarcinoma. The primary curative approach for esophageal cancer involves esophagectomy, which, when coupled with neoadjuvant therapy, can result in a five-year survival rate exceeding 50%(1). This is one of the most complication laden operations in gastrointestinal surgery and anastomotic leak, when the coupling of the gastric remnant to the esophagus fails to heal completely, entails significant morbidity and suffering for the patient. The consequences of an anastomotic leak still pose a formidable challenge to caregivers and any step to decrease the risk of this occurring, carries high value clinically and scientifically(2).

Esophagectomy has also been linked to significant postoperative thoracic pain, primarily due to intercostal incisions. This pain can lead to reduced mobility, pulmonary complications, and delayed recovery, underscoring the importance of effective postoperative pain management(3). Currently, thoracic epidural analgesia stands as the preferred method for managing pain in these cases and is an integral part of many enhanced recovery protocols, offering better outcomes in pain control and reduction of pulmonary complications compared to systemic opioids(4). However, epidural has also been linked with intra- and postoperative hypotension due to the splanchnic sympathetic blockade, which can reduce preload to the heart and the central blood volume. Treatment of hypotension caused by epidural analgesia may include use of vasopressors or fluid resuscitation(5), which again have been speculated to cause postoperative complications, including anastomotic leak(6).

The advent and introduction of minimally invasive esophagectomy (MIE) techniques, which are associated with less postoperative pain compared to open surgery, alongside the implementation of enhanced recovery protocols aimed at expediting mobilization and recovery post-MIE, challenges the traditional reliance on epidural analgesia. This is due to the abovementioned potential adverse effects along with others such as failed catheter placement, and reduced mobility, which could hinder the goals of enhanced recovery protocols.

Past systematic reviews on postoperative pain management focusing on patients undergoing various thoracotomy or thoracoscopy procedures, predominantly lung surgeries, have indicated that paravertebral analgesia might offer comparable pain relief to epidural analgesia but with fewer side effects such as hypotension, urinary retention, and nausea(7). However, transthoracic esophagectomy involves both an abdominal and thoracic phase, which means these findings might not fully apply to esophagectomy patients. Preliminary systematic reviews exploring paravertebral analgesia in esophagectomy patients suggest it offers similar pain control and potentially fewer hypotensive events than epidural analgesia. Nevertheless, these reviews also point out the current gap in high-quality prospective research specifically focusing on MIE patients, highlighting an area in need of further investigation(8). A recent trial comparing epidural analgesia to paravertebral block shows comparable pain relief but more anastomotic leaks in the epidural group(9). However, the trial was not powered for this outcome and the difference was not significant. We therefore aim to launch a trial with superiority design regarding anastomotic leak.

Trial ID:	ISRCTN16853684
Version No:	1.0
Date:	January 27 th 2026

## 5.1 Benefit-risk evaluation

Both treatment methods are in clinical use today and have been scientifically and clinically evaluated and deemed safe (8-11). The participation in this trial will therefore not go outside clinical routine in reference to medical treatment.

Even if the investigational procedure in this trial, i.e., no epidural analgesia and paravertebral block, has been demonstrated feasible and safe, there are possible disadvantages and complications, such as suboptimal pain-control and paracostal bleedings, but the standard procedure (epidural analgesia) is not free from side-effects and we consider no additional risk to be added in the interventional arm of this trial. There is ample experience in management of all the potential complications in the interventional arm (paravertebral block) and in the control arm (epidural analgesia). All patients will be followed closely regarding all outcomes, including complications.

There will be some additional questionnaires to assess pain relief and patient-reported postoperative recovery (QoR15, see Appendix 2), but the added discomfort of this is deemed to be minimal.

In addition, an independent data safety and monitoring board will perform evaluations after 100 and 250 patients are included.

The results of the BALANCE trial are expected to provide medical staff with evidence-based guidance to optimize care during esophagectomy. Given that enrolled patients will receive treatments that are currently used in clinical practice and considered safe, the Sponsor concludes that the potential benefits of the trial outweigh any associated risks.

## 6 Trial objectives

### 6.1 Primary objectives

To compare safety (superior-less anastomotic leak) of paravertebral block compared to the current routine of epidural analgesia in minimally invasive esophagectomy for malignant disease.

### 6.2 Secondary objectives

The secondary objectives of the trial are to compare the difference, if any, between paravertebral block analgesia and epidural analgesia in:

1. Postoperative pain
2. Patient-reported quality of postoperative recovery
3. Risk of overall and procedure-specific complications
4. Prevalence of hypotension
5. Time to unassisted ambulatory mobilization
6. Time in operating theatre
7. Duration of surgery
8. Fluid retention
9. Length of hospital stay
10. Time in high-dependency unit
11. Overall survival

Trial ID:	ISRCTN16853684
Version No:	1.0
Date:	January 27 th 2026

## 6.3 Primary endpoint

Anastomotic leak will be recorded at postoperative day 30 when completing the electronic Case Report Form (eCRF). Any subclinical leaks will also be recorded (mandatory CT peroral contrast day 7).

## 6.4 Secondary endpoints

[figure not shown]
The secondary endpoints of this trial are:

1. Investigation of acute postoperative pain evaluated with NRS at baseline and on day 1, 2, 3, 7 and 30 after surgery (Appendix 1); and total postoperative opioid use (enteral and parenteral), recorded at postoperative day 30. Patient-reported outcomes evaluated with QoR15(12) on day 1, 2, 3, 7 and 30 after surgery (Appendix 2).
2. Risk of overall and procedure-specific complications recorded at postoperative day 30:
  - Overall complications according to Clavien-Dindo (13)
  - Rescue (intervention group)/re-insertion (control group) of EDA (Y/N)
  - Pneumonia
3. Assessment of blood pressure up to postoperative day 5
4. Time to first day of unassisted movement
5. Total operation time
6. Total time used in operation theater
7. Patient weight assessed on baseline, day 1, 2, 3 and 7
8. Postoperative number of days in hospital
9. Postoperative number of days in high-dependency unit
10. Time from surgery to all-cause death

## 7 Trial design and procedures

### 7.1 Overall trial design

The BALANCE trial is an open-label, randomized, controlled, phase III, multicenter trial evaluating the paravertebral block technique with local anesthesia combined with patient-controlled analgesia with opioids, compared to the standard technique of thoracic epidural analgesia (local regime if within boundaries of the trial):

## 7.2 Procedures and flowchart

Procedure	Screening Preoperative inclusion visit	Operation Baseline information and randomization	Postoperative day 1, 2, 3 and 7	Postop Day 30 (28-35)g	3 and 5 years postop
Incl/exclusion criteria	✓				
Informed consent	✓				
Medical history/concomitant medications	✓	✓			
Randomizationa	✓	✓			
Anastomotic leak			Day 7 b	✓ c	
Pain scored	✓		✓	✓	
Patient reported outcomee			✓	✓	
Weight	✓		✓	✓	
Registration of all secondary endpointsf				✓	
Registration of start of epidural and cumulative hours with vasopressor use				✓	
Survival data					✓

a Patients are randomized no later than 12h before surgery

b One CT scan to be performed on postoperative day 7

c All diagnosed anastomotic leaks will be recorded in the eCRF

d Measured using NRS

e Reported with QoR15

f Recorded secondary endpoints include: postoperative opioid use, overall complications according to Clavien-Dindo, rescue or reinsertion of EDA, pneumonia, hypotension, first day of unassisted movement, total operation time, total time in operating theater, days in hospital, and days in high-dependency unit

g Data completion of eCRF is ideally obtained at day 30, but a one-week variance is accepted (day of data completion is noted in the eCRF)

Trial ID:	ISRCTN16853684
Version No:	1.0
Date:	January 27 th 2026

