# 10 Methods for measurement of endpoints for clinical efficacy and safety

Baseline data will be collected in an electronic randomization module where clinical information and stratification variables will be entered by the site investigator no later than the day before surgery. An eCRF will be filled out for all outcomes at the first postoperative visit, 30 days postop. All study data will be transferred from the eCRF to the study database. Additional outcome data (survival) will be accrued at 3 and 5 years and added to the study database.

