## 10.1 Methods for measurement

### 10.1.1 Primary endpoint

The primary endpoint of anastomotic leak will be assessed according to local routines. A CT with contrast swallow is performed on postoperative day 7. If this CT is not performed (prior CT performed on clinical suspicion or other reason), this is specified. When the eCRF is filled out, all anastomotic leaks up to 30 days will be recorded, including day of onset. The questions regarding the primary outcome will be:

- Anastomotic leak (yes/no)
- Anastomotic leak type (grade I-III according to Low et al.(14))
- Day of a diagnosed anastomotic leak (1-30/NA)

Trial ID:	ISRCTN16853684
Version No:	1.0
Date:	January 27 th 2026

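### The day-30 form may be completed from day 28, before the 30-day leak period has closed, and no later check of leak status is described (minor)

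*Protocol*

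**What the plan says.** The endpoint period is fixed at 30 days. The synopsis (section 4) gives the primary endpoint as "Anastomotic leak assessed up to 30 days after surgery". Section 10.1.1 says: "When the eCRF is filled out, all anastomotic leaks up to 30 days will be recorded, including day of onset", and it limits the day field to 30: "Day of a diagnosed anastomotic leak (1-30/NA".

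The recording is tied to one form. Section 6.3: "Anastomotic leak will be recorded at postoperative day 30 when completing the electronic Case Report Form (eCRF". Section 10: "An eCRF will be filled out for all outcomes at the first postoperative visit, 30 days postop", with no tolerance stated there. After that, sections 10 and 14.1 describe only a survival update at 3 and 5 years.

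The tolerance appears only in section 7.2. The column header reads "Postop Day 30 (28-35", and footnote g to that header reads "Data completion of eCRF is ideally obtained at day 30, but a one-week variance is accepted (day of data completion is noted in the eCRF".

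For the other outcomes, section 6.4 lists "total postoperative opioid use (enteral and parenteral), recorded at postoperative day 30", and the synopsis defines every secondary outcome outside pain and patient-reported measures, survival excepted, at postoperative day 30.

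**The concern.** A form that carries the primary endpoint should not be allowed to be finished before the endpoint period is over. Under section 7.2 it can be. A leak first diagnosed on day 29 or 30, after the form was completed on day 28, has no described route into the data, so the patient may remain recorded as leak-free. The noted completion day shows that observation was short but does not supply the event. This is a rule about data capture, so an analysis plan could not repair it afterwards.

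The wording of footnote g adds uncertainty about how early is too early. Two sites could apply different windows, each with support in the text.

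**Working it through.** **The window against the endpoint period**

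| Reading | Earliest compliant day | Days of the 30 not yet observed | Latest day |
|---|---|---|---|
| Header, 28-35 | 28 | 29 and 30: 2/30 = 6.7% | 35 |
| Footnote g as total width | 28 (35 − 28 = 7 days, agrees with the header) | 2/30 = 6.7% | 35 |
| Footnote g as ±7 days around day 30 | 23 | 24 to 30: 7/30 = 23% | 37 |

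Every reading opens before day 30. The header and the footnote agree if the week is a total width, and differ only if it is a plus-or-minus tolerance. The footnote does not say which.

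**The plan's own figure (section 13.1)**

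Inputs: 15% against 7.5% leak, 80% power, 5% significance (section 13.1), two-sided (section 13.3), 1:1 allocation (section 9.1).

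Unpooled variance: n = (1.960 + 0.842)² × (0.15 × 0.85 + 0.075 × 0.925) / 0.075² = 7.849 × 0.196875 / 0.005625 = 274.7, so 275 per arm. This reproduces the stated 275. The pooled-variance formula gives 278.

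Expected leaks: 275 × 0.15 + 275 × 0.075 = 41.25 + 20.625 = 61.9, about 62.

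Power at 275 per arm, pooled test: Φ{[Δ√n − 1.960 × √(2p̄(1 − p̄))] / √(p₁(1 − p₁) + p₂(1 − p₂))}. With Δ = 0.075 and p̄ = 0.1125 this is Φ{(1.2437 − 0.8758) / 0.4437} = Φ(0.829) = 79.6%.

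**Sensitivity to lost leaks**

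Let f be the share of all leaks lost because the form was completed first. The protocol gives no leak-onset distribution, so f is an assumption. Both leak rates are multiplied by (1 − f), as if the loss were equal in both arms:

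| f | Leaks lost (f × 61.9) | Rates | Power at 275 per arm |
|---|---|---|---|
| 0 | 0 | 15% / 7.5% | 79.6% |
| 1% | 0.6 | 14.85% / 7.425% | 79.2% |
| 2% | 1.2 | 14.7% / 7.35% | 78.7% |
| 5% | 3.1 | 14.25% / 7.125% | 77.3% |

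To be lost, a leak must be diagnosed after the form was completed, and the form must not be updated. If only some forms are completed early, f is smaller than the share of leaks diagnosed in the exposed days.

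**The case against.** Four arguments can be made against the point, and each limits it.

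- **The header and footnote do not contradict each other.** A reader might infer that they do. Days 28 to 35 span exactly one week, and the footnote is attached to that header. The text supports ambiguity only, so the 7-day gap is a possible reading and not the plan's stated window.
- **Nothing says the form is locked at completion.** A reader might infer that late leaks are certainly lost. Section 10.1.1 requires all leaks up to 30 days to be recorded. Section 14.3 has a monitor check the forms against hospital records, and section 14.2 locks the database only once it is declared complete and accurate. A late leak can therefore be missed, but it need not be. What stands is that no step is described whose purpose is to confirm leak status through day 30.
- **Cumulative outcomes have a day-30 definition.** A reader might infer that opioid totals, complications and days of stay run to whatever day the form is filled in, so that periods differ between patients. The synopsis largely answers this. What remains is practical: section 10.1.2 lists no cut-off for the opioid total or days of stay, and no event date for complications, so the form should carry the synopsis definition.
- **The window is the same in both arms.** A reader might infer bias because the trial is open-label. Nothing in the protocol makes completion timing differ by arm. Late completion cannot inflate the primary endpoint either, because the leak day stops at 30.

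**Conclusion.** The point holds in a limited form. Section 7.2 accepts completion of the only leak form up to 2 days before the 30-day period ends, and no re-check of leak status is described. Footnote g is ambiguous and, on its wider reading, would extend the gap to 7 days.

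The size is small. With 1-5% of about 62 leaks lost in both arms, 0.6-3.1 events are missed and power drops by about 0.5 to 2.3 percentage points from 79.6%. That rests on the planned leak rates, 275 per arm, equal loss in both arms and an assumed share lost. The sample size calculation itself is not affected. Severity is minor. It is worth correcting because the change costs almost nothing at version 1.0.

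**What to change.** - In section 7.2, give one unambiguous window for completing the form that starts on or after day 30, for example days 30-37. Alternatively, keep the visit window and require leak status to be confirmed through day 30, by contact or record check, before the form is final.
- Reword footnote g so that it states the same window in days.
- In the eCRF, apply the synopsis definition to the cumulative items: opioid total, complications, hospital days and high-dependency days are entered as of postoperative day 30, whatever the completion date. A date check can enforce the earliest completion day.

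Cost: a few words in the flowchart and a form check. Some visits or record checks that would have fallen on day 28 or 29 move by one or two days.

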## 7.3 Start, end, temporary halt, and early termination

### 7.3.1 Start of the clinical trial

The start of the trial is defined as the first act of recruitment of a potential subject.

### 7.3.2 Temporary halt or early termination

The trial may be prematurely terminated for safety reasons affecting the risk-benefit balance or if the recruitment of subjects cannot be completed within reasonable time. Decisions on premature termination are taken by the sponsor.

If the trial is prematurely terminated or suspended, the investigator should immediately inform the subjects and ensure appropriate treatment and follow-up.

### 7.3.3 End of the clinical trial

The trial ends when the last subject has completed the last follow-up, died or withdrawn consent, or is lost to follow-up. The estimated time for last follow-up (survival) is Q3 2033.

## 8 Subject selection

### 8.1 Inclusion criteria

To be included in the trial, subjects must meet all of the following criteria:

- $\geq 18$  years of age
- Planned thoracoabdominal total minimally invasive resection for histopathologically confirmed esophageal or GEJ cancer in locally advanced stages (cT1a N+ or cT1b-4a any N; M0-1)
- Performance status ECOG 0-1
- Signed informed consent

### 8.2 Exclusion criteria

Subjects must not be included in this trial if any of the following criteria are met:

- Epidural analgesia contraindicated, i.e., known uncontrollable hypersensitivity to the components of the chemotherapeutic agents used in the trial regimens or anatomical factors precluding epidural catheter placement
- Use of anticoagulants precluding EDA use
- No planned postoperative use of nasogastric tube
- No ability to understand the study in terms of risk and benefits (including language difficulties)
- The subject has any other severe acute or chronic medical or psychiatric condition or laboratory abnormality that would, in the judgment of the investigator, pose excess risk associated with study participation or that, in the judgment of the investigator, would make the patient inappropriate for entry into the trial.

Trial ID:	ISRCTN16853684
Version No:	1.0
Date:	January 27 th 2026

## 8.3 Screening

Subject eligibility (that subjects fulfil all inclusion criteria and do not meet any exclusion criteria) is established before participation in the study. This screening will take place when surgery is planned and no later than the day before surgery.

Documented informed consent must be provided before performing any protocol-specific procedure.

## 8.4 Withdrawal criteria

Subjects can discontinue their participation in the trial at any time without any consequence to his/her continued treatment. The investigator/sponsor can at any time terminate the trial for a subject due to, e.g., unacceptable adverse events/adverse reactions or because the subject does not follow procedures in the clinical trial protocol. If the subject discontinues the trial, follow-up of this subject will be performed according to the clinical routine of the study site in question.

Specific reasons for discontinuing a subject for further assessments include:

- Withdrawal of informed consent.
- Not fulfilling the inclusion/exclusion criteria as stated above (incorrectly included).
- No resection performed (reason specified)
- Operation was converted to open surgery
- If the investigator considers it not to be in the subject's best interest to continue participation in the study (e.g. due to non-tolerable adverse reactions or serious adverse events (SAEs) during surgery).
- If there is a significant protocol deviation.

A discontinued subject should be asked to come to the clinic for a final assessment, if possible. The reason for subject discontinuation will be documented in the eCRF. The sponsor has the right to keep and use all data that has been collected up until the time that the subject discontinues study participation. A study subject who has been randomized and who is withdrawn from the study will not be replaced.

